1.0 Background and Purpose

The misuse of and addiction to opioid medications has become the most rapidly increasing drug problem in the US, which has consequences for pregnant mothers and their babies. The prevalence of maternal opioid drug use at the time of delivery in California is approximately one percent. The neonatal abstinence syndrome (**NAS**) is a constellation of narcotic drug withdrawal symptoms that develops in 42 to 94 percent of infants born to narcotic dependent mothers. There are no preventative treatments for this severe syndrome, which can result in a prolonged hospitalization and treatment in a neonatal intensive care unit.

Based upon a genetic discovery, we demonstrated that administration of a 5-HT3 antagonist (ondansetron) prevented the symptoms of narcotic drug withdrawal in experimental studies in mice and in humans. From this, we hypothesize that ondansetron administration to pregnant narcotic-using mothers just prior to delivery, followed by a 3 to 5-day period of ondansetron

administration to the neonate, could reduce the incidence or severity of NAS symptoms. Ondansetron is a broadly utilized drug with a substantial safety record in pregnant women. We now understand the pharmacokinetics of ondansetron at birth based on PK analysis of placental and neonatal blood samples in babies whose mothers' were given ondansetron prophylactically prior to cesarean delivery (Aim 1 of the protocol, Prevention of Neonatal Abstinence Syndrome). In this study, (Aim 2) we will conduct a multi-center, randomized, double blind, and placebo-controlled trial to determine whether ondansetron treatment will reduce the incidence (percentage of infants requiring narcotic drug treatment) or severity (total amount of narcotic drug required, length of hospitalization, symptom severity scores) of NAS in babies born to narcotic-using mothers.

This project tests a very novel approach for preventing an important pregnancy-related complication of narcotic drug abuse. If a brief period of ondansetron administration to the mothers that use narcotic drugs, and to their babies, can prevent or ameliorate the development of narcotic drug withdrawal symptoms in neonates, this would reduce human suffering and the growing societal cost of opiate abuse.

2.0 Protection of Human Subjects

2.1 Risks to Human Subjects

2.1.1 Human Subjects Involvement, Characteristics, and Design

This study will include up to 120 opioid-addicted, otherwise healthy and with no cardiac history of prolongation of the QTc interval, 18-45 years of age, pregnant women \geq 37 weeks through < 42 weeks gestation and their newborns. Subjects will be recruited from about 5-10 sites around the country with some hospitals joining the study and then dropping out if they are not able to enroll enough subjects. Locally, we are enrolling at two Bay Area hospitals: Lucile Packard Children's Hospital at Stanford and Santa Clara Valley Medical Center. The sites outside of California are: Johns Hopkins Bayview Medical Center in Baltimore, Maryland, the University of Tennessee Health Science Center in Memphis, Tennessee, the University of Louisville in Louisville, Kentucky, and Thomas Jefferson University Hospital in Philadelphia, Pennsylvania.

Informed consent will be obtained by either a member of the research team or a member of the participant's medical team during the course of her prenatal care with her obstetrician or at a pre-scheduled visit with the anesthesiologist prior to delivery, or lastly, and the least likely time to get consent may be on admission to labor and delivery, only if time allows true informed consent in that setting. Because this study involves the newborn infant, as well as the mother, consent will be obtained from both parents where fathers are involved and competent to provide consent. After admission to the labor and delivery suite, the mother-infant pair will be randomized to one of two treatment groups (placebo or ondansetron) by the pharmacy. Randomization will be done between all sites to ensure that the first 20 mother-infant pairs enrolled will have an equal number of placebo and active treatment participants. The medical team, the research team, and the participant will be blinded to the treatment assignment (double-blind study). The pharmacy will hold the key to the treatment assignment and will un-blind the study only if deemed medically necessary.

A. Safety Monitoring of Participants:

1. Neonates admitted to Well Baby Nursery:

- a. ECG: The neonate will be stabilized after birth and then will receive a screening 12-lead ECG to rule out QTc Bazett greater than or equal to 480ms. Once the neonate is medically stable and a normal QTc confirmed by the treating physician, the neonate will receive the same 'blinded' study drug (ondansetron or placebo) as his or her mother; this first dose of study drug is to be given between 4-8 hours after delivery. A repeat 12-lead ECG will be done on all neonates following each of the 5 doses of study drug, between 2-5 hours after each dose of study drug. Any neonate that shows significant ECG changes will be excluded from further dosing of study medication but will continue safety follow-up.
 - i. If the QTc is prolonged, the neonate will be transferred to the NICU for continuous cardiac monitoring, if the standard of care indicates the neonate should be admitted to NICU; this will be determined on a case-by-case basis at each site. In addition, a blood test to check the potassium, magnesium, calcium, and ionized calcium levels will be done if the clinical team believe it is necessary for the neonates safety; if the levels are abnormal, electrolytes will be normalized using IV or oral supplements as indicated per standard of care.
 - ii. All ECGs, from all sites, will be sent to Stanford to be interpreted by a cardiologist, who is not a member of the study team, to confirm the accuracy, and consistency of the initial readings.
- b. Standard of Care for Well Baby Nursery:
 - i. Vital Signs: heart rate (HR), respiratory rate (RR), and temperature will be monitored every 4-8 hours depending on the infant's history, and blood pressure at least once per day.
 1. If the HR is less than 80 beats per minute, a rhythm strip or 12-lead ECG is ordered to evaluate the QTc interval, a Neonatal Intensive Care Unit (NICU) physician will assess the neonate and a blood pressure will be obtained.
 2. If the QTc is prolonged, see "ECG" above which discusses the possibility of the neonate being transferred to the NICU for continuous cardiac monitoring if deemed necessary by standard of care
 - ii. A member of the study team will visit the Well Baby Nursery at least once per day to ensure the neonate is doing well and that everyone on the clinical team understands the protocol and knows how to contact the principal investigator to answer questions as needed.
 - iii. Modified Finnegan Evaluation (Scoring) to be done per standard of care at each institution since they are all similar and have been in place for many years. Each site involved in this study has established guidelines for starting, advancing and weaning treatment for NAS (see attached guidelines for each site). All the data regarding the treatment for NAS will be collected for the study.

2. Neonates Admitted to the NICU after Birth:

- a. ECG, Vital Signs, and Pulse Oximetry: the neonate will be stabilized after birth and then will receive a screening 12-lead ECG to rule out QTc Bazett greater than or equal to 480ms. Once the neonate is medically stable and a normal QTc confirmed by the treating physician, the neonate will receive the same study drug (ondansetron or placebo) as his or her mother; this first dose of study drug is to be given between 4-8 hours after delivery. A repeat 12-lead ECG will be done on all neonates following each of the 5 doses of study drug, between 2-5 hours after each dose of study drug. Any neonate that shows significant ECG changes will be excluded from further dosing of study medication but will continue safety follow-up
- b. Standard of Care for the NICU:
 - i. Blood pressure is measured at least once per shift. Depending on acuity and access, blood pressure will be monitored either continuously (if indwelling line is indicated for clinical care) or every 4-8 hours using non-invasive oscillometry.
 - ii. Continuous ECG, heart rate, respiratory rate and oxygen saturation monitoring are done on all NICU patients; the HR, RR, and oxygen saturations are documented in the medical record every 1-4 hours as per standard of care, with vitals documented more frequently in acutely ill infants.
 - iii. A member of the study team will visit the NICU at least once per day to ensure the neonate is doing well and that everyone on the clinical team understands the protocol and knows how to contact the principal investigator to answer questions as needed.
 - iv. Modified Finnegan Evaluation (Scoring) to be done per standard of care at each institution since they are all similar and have been in place for many years. Each site involved in this study has established guidelines for starting, advancing and weaning treatment for NAS (see attached guidelines for each site). All the data regarding the treatment for NAS will be collected for the study.

Interim Analysis: an interim analysis will be performed after a total of twenty (20) pregnant women and their twenty (20) neonates have been enrolled and dosed with study medication. The analysis will include all the ECG measurements, blood concentration levels for pharmacokinetics (PK) and a reassessment of the PK of ondansetron in neonates, all to be reviewed by the DSMB. The study will only proceed if the DSMB gives their approval. These 20 neonates will be the “First cohort” of neonatal patients. (Note, this was done between April and May 2016)

B. Study Medication Dosing

Adult Pregnant Participant’s Dose: The amount and timing of the dose of ondansetron to be administered to the pregnant participants, who are randomized to the ondansetron group, will be 8 mg (IV) within 4 hours of delivery. Should the participant be undelivered 4 hours following the initial dose of study drug, a second dose will be administered. The study medication will be delivered intravenously to the mother prior to either vaginal or cesarean delivery. Exception: if the pregnant participant does not want to receive any study medication prior to delivery because she is not experiencing nausea, she may still continue to be a part of the study and her neonate will be assigned to the study medication she would have been randomized to receive. This allows for an adult patient to not be given the study medication

(ondansetron or placebo) if they feel they do not need it. The neonate's participation will continue as planned.

Neonatal Participant's Dose: The neonates who are born to the mothers, who are randomized to receive ondansetron, will have an initial oral dose of ondansetron 0.07 mg/kg given between 4-8 hours after delivery. The subsequent doses of ondansetron will be 0.07 mg/kg orally every 24 hours for up to 5 doses maximum.

The timing and volume of placebo administration for the 50% of subjects in the placebo group will mimic that of the 50% of subjects in the ondansetron group. Placebo will consist of either normal saline for IV administration or inactive oral syrup for oral administration.

For those neonates who require an intravenous catheter for any other medical reason, these neonates will receive an ondansetron dose of 0.04 mg/kg IV every 24 hours for up to 5 doses maximum.

C. Study Procedures

Adult Pregnant Participant's Procedures:

1. Maternal blood for ondansetron concentration (PK) will be collected within 30 minutes of delivery (either pre- or post-delivery).
2. Maternal urine will be collected for toxicology analysis prior to delivery to identify possible polysubstance abuse (polysubstance use is not an exclusion criteria)
3. Once delivery is complete, the mother's participation will consist mainly of answering questions about her own medication use and the baby's feeding habits over the remainder of the study while the neonate participates in the study.

Neonatal Participant's Procedures:

1. The Modified Finnegan scoring system will be used to evaluate neonates for symptoms of NAS at each site involved in the study and is considered standard-of-care for babies who are at risk for NAS. Treatment with the study medication will continue for a maximum of five days (starting within approximately 4-8 hours after birth).
2. Treatment of NAS: morphine will be the first treatment choice before other treatment medication choices (opioid or non-opioid) for NAS symptoms. This is the standard-of-care at all participating sites. Each site involved has established guidelines for starting, advancing and weaning treatment for NAS. Any medication used to treat the symptoms of NAS will be noted as to name, dose, route, reason for dosage (Finnegan score or other reason) and time of administration. If the neonate develops nausea and clinical treatment of the nausea would include ondansetron then an alternate antiemetic should be considered. The infant may already have a full therapeutic level of ondansetron and additional dosage will not help treat the nausea. Ondansetron is not strictly contraindicated by this protocol as some neonates will have received placebo. For those infants that have been randomized to ondansetron, an additional dose of ondansetron will not be harmful.
3. 12-Lead ECG: all neonates, whether they are cared for in Well Baby Nursery or the NICU, will have a screening 12-lead ECG prior to their first dose of study drug and a follow-up 12-lead ECG within 2- 5 hours after each dose of study drug.

4. Umbilical cord blood (venous) will be collected at delivery and evaluated for ondansetron and ondansetron metabolite concentration. The standard of care at most hospitals is to discard the umbilical cord in the hospital biological waste system unless the parents have asked for it to be saved. We will only take these cord samples if the mother agrees to let us have them.

5. Blood Samples: between one (1) and nine (9) 0.1 mL blood samples (about 1-3 drops) will be collected from the neonate after birth to measure ondansetron and metabolite concentrations. These samples will be collected during clinically indicated blood sampling whenever possible to prevent additional trauma to the infant. When and if an intravenous cannula is inserted for administration of other treatments and then the study drug, a blood sample may be obtained during the insertion of this cannula, if possible, to avoid a heel stick for the PK blood draw done prior to starting IV dosing of study drug. If there are no clinically indicated blood draws ordered for a neonate in the first 12 hours of life, it may be necessary for one or two of these research PK samples to be drawn separately from clinically indicated sampling. For example, if there are no clinically indicated labs that need to be done prior to the first dose of study drug, then the first PK sample of blood would be done for research only, if the mother agrees to a heel stick. The second PK sample is scheduled to be drawn after the first dose of study drug but before the infant is 12 hours old and that would be an extra heel stick if there are no clinically ordered labs during this time period. During the following days of treatment, additional 0.1 ml of blood will be obtained when clinically indicated blood sampling occurs up to a grand total of 9 times during the study. Times will be noted to the nearest minute for all blood samples.

6. Follow-up calls/visits: a research team member will call the mother of the baby once they have been discharged home, if the baby is discharged prior to Day 15 of their life. We want to follow up on the babies and learn how they are doing and make sure they are not going into "Delayed" NAS. For babies who are discharged early it is more likely they could go into delayed NAS and that is why we plan to call the mothers daily, for up to 10 days after the baby takes their last dose of study medication, to ask about their baby's status. We are interested in how the baby is feeding, are they breast or bottle feeding the baby, what is the baby's mood (crying excessively, fussy, agitated), sleeps for how many hours after feeding, sneezing a lot, sweating, vomiting, gaining weight, loose stools or watery stools, etc. We also need to ask the mother all the medications she is taking, if she is breastfeeding her baby, since we know these medications will enter the baby's system through the breast milk. If a baby is not discharged before day 15 of their life, the research team member will visit the baby in the hospital daily, for 10 days after their last dose of study drug, to check on the status of the baby from the clinical team caring for the baby. If the mother is home while the baby remains hospitalized, the research team member will also call the mother on a daily basis to maintain contact and to ask the mother all the medications she is taking if she is breastfeeding her baby (we know these medications may enter the baby's system through the breast milk).

7. The final follow-up call (or visit if the baby is still in the hospital) will occur approximately 30 days after the baby's last dose of study medication; this call (or visit) will be to determine if any previously reported adverse events have resolved and/or if any new adverse events have occurred since the last follow-up call or visit.

The primary endpoint will be the incidence of NAS in enrolled neonates and will be measured by the need for pharmacologic treatment for the symptoms of NAS (Morphine). The secondary endpoint of the severity of NAS will be measured by the length of the hospitalization (birth to discharge), the total dose of narcotic required to treat the symptoms of NAS, and the need to include barbiturates in the treatment of symptoms of NAS.

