2.1.2 Inclusion/Exclusion

Criteria

Subjects	Inclusion Criteria	Exclusion Criteria
Maternal/Paternal	Women of reproductive age (18-45 years old, inclusive) and their fetuses/neonates. Daily opioid use for at least 3 weeks prior to delivery Gestational age of \geq 37 weeks to < 42 weeks at delivery. Competent mother willing to sign the informed consent for herself and both parents competent and willing to sign consent/permission for their neonate.	Any condition that, in the opinion of the investigator, would compromise the health of the participant (both mother and fetus) or the integrity of the data. Known allergy to the study medication. Screening 12-lead ECG, if done, showing prolonged QTc will stop the mother from receiving any study drug but her neonate can still be included in the study. Maternal ingestion or administration of ondansetron within 24 hours prior to delivery, for reasons other than study purposes, will exclude the mother and neonate.
Neonatal	Participating mother Maternal (and paternal if	QTcB greater than or equal to 480ms on any 12-lead

	present and competent) consent	ECG post delivery will stop the dosing of the study drug, but safety follow up will be done including blood samples & 12-lead ECG(s) if the mother or baby received at least one dose of study drug.
--	-----------------------------------	---

This study will include special classes of participants: pregnant women and their newborns. The focus of this study is specific to these sensitive populations of pregnant women and neonates and as such warrants their inclusion. We feel that, in balance, the potential for significant benefit to the neonatal population in this study and in future patients outweighs the risks (section 5.0 *Potential Risks* below).

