To Neonate Risk is no greater than placebo risk To minimize risk, screen for QT prolongation and give dose (determined in Aim 1) to reach blood level predicted to have desired clinical effect Dose will be within dose limits studied in slightly older infants (less than 0.15 mg/hr in 12hours) Duration of exposure will be minimized by stopping study drug after a maximum of five days of study drug treatment, Will be discontinued if related adverse events occur If QTc interval abnormalities occur or a neonate has QTcB greater than or equal to 480 ms, the neonate's study drug will be stopped and no further dosing will occur; follow up 'safety' EKGs will be done until the QTc has returned to 479ms or less, if possible. All neonates will have a screening ECG prior to their first dose of study medication & an ECG after each dose for a maximum of 6 ECGs in 5 days.
Delayed onset of NAS
To Mother Not applicable
To Fetus Risk will be managed by educating the parents about the NAS symptoms Provide parents with contact information for both their clinical caregivers and the research team Ask parents to report delayed onset to both groups Appropriate medical care will be provided Parents may receive a maximum of 10 daily follow-up telephone calls if the baby is discharged before Day 15 of life; the calls are being done to review continuation or recurrence of NAS symptoms and the occurrence of other adverse events. The research staff will call daily, through a maximum of 10 days after the last dose of study drug. If the baby is still in the hospital through Day 15 of life, this information will be gathered by the research staff visiting the neonate in the hospital. The final follow-up phone call to the parents will occur approximately 30 days after the baby's last dose of study medication to check for any occurrence of new adverse events and to inquire about the resolution of any previously reported adverse events.
To Neonate Not applicable
Phlebotomy
To Mother Minimize risks of hematoma and infection by following all hospital guidelines including using aseptic technique and applying pressure to site after sample collection Only qualified personnel may collect blood samples for analysis
To Fetus Not applicable

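### The neonatal QTc stop covers study drug only, and the antiemetic paragraph leaves clinical ondansetron open to an infant already stopped

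*Protocol*

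**What the plan says.** The neonatal QTc stop appears in three sections of the protocol.

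- Section 2.1.1 A, with the same wording for the Well Baby Nursery and the NICU: "Any neonate that shows significant ECG changes will be excluded from further dosing of study medication".
- Section 2.1.2, Neonatal, where the trigger is QTcB of 480 ms or more on any 12-lead recording: "ECG post delivery will stop the dosing of the study drug". Safety follow-up, including ECGs, continues.
- Section 6.2, Ondansetron, To Neonate: "study drug will be stopped and no further dosing will occur". After that, safety "EKGs will be done until the QTc has returned to 479ms or less, if possible".

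Ondansetron given for clinical reasons is handled elsewhere, in section 2.1.1 C, Neonatal Participant's Procedures, item 2. If an infant becomes nauseated and "clinical treatment of the nausea would include ondansetron then an alternate antiemetic should be considered". The stated reason is that the infant may already have a therapeutic level, so more drug would not help. The item continues: "Ondansetron is not strictly contraindicated by this protocol as some neonates will have received placebo". It ends: "For those infants that have been randomized to ondansetron, an additional dose of ondansetron will not be harmful".

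The SAP does not address non-study ondansetron in infants.

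**The concern.** QTc prolongation is the neonatal hazard that this protocol watches most closely. It requires a screening ECG, an ECG after each study dose, central reading by an independent cardiologist, and DSMB review of all ECGs from the first 20 pairs. An infant who crosses the threshold has blinded study drug withheld because it may be ondansetron. The nausea paragraph leaves the same compound available to that infant through the clinical route and offers an unqualified reassurance about harm.

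A reader of that paragraph gets no cardiac warning. The reassurance is addressed to infants in the ondansetron arm, but the clinical team is blinded and cannot tell which infants those are, so at the bedside it reads as a statement about any enrolled infant. At stake is a further dose of a drug the trial monitors for QT effect, given to an infant already known to have a prolonged QTc.

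**Working it through.** This is mainly a comparison of texts. The only arithmetic is an illustration of how often the situation might arise.

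**Step 1: what the stop covers.** Sections 2.1.1 A and 2.1.2 both limit it to study medication. In section 6.2 the clause about no further dosing could be read more widely, but its subject is the neonate's study drug, and the other two sections support the narrow reading. None of the three names ondansetron prescribed clinically.

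**Step 2: what the nausea paragraph excepts.** Nothing. It refers to neither QTc nor an infant whose study drug has been stopped. Its preference for another antiemetic is advisory and rests on lack of added benefit.

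**Step 3: whether another provision closes the gap.**
- Management of a prolonged QTc (section 2.1.1 A) consists of NICU transfer decided case by case, cardiac monitoring, and electrolyte testing and correction where the team judges it necessary. Avoiding ondansetron is not listed.
- The scheduled post-dose ECGs, 2 to 5 hours after dosing, follow doses of study drug. A clinical dose triggers none. A stopped infant does have the safety ECGs of sections 2.1.2 and 6.2, and a NICU infant has continuous ECG monitoring.
- Un-blinding is available if medically necessary (section 2.1.1), but it is not tied to a decision to give ondansetron.

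These provisions lower the risk and help to detect a problem. None bars the dose.

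**Step 4: the threshold itself.** It is consistent: stop at 480 ms or more, and safety ECGs until 479 ms or less. The problem lies in which drug is stopped, not in the number.

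**Step 5: illustrative frequency.** The documents give no rate for QTcB of 480 ms or more, and none for nausea treated with ondansetron. Assume 1-5% and 1-10% respectively, independent of each other, among the 120 planned neonates (section 12).

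Expected infants with both = 120 × P(QTc stop) × P(nausea treated with ondansetron)

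- Low end: 120 × 0.01 × 0.01 = 0.012
- High end: 120 × 0.05 × 0.10 = 0.6

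Fewer than one infant is expected across the assumed range. The independence assumption probably overstates the figure, because a team aware of a prolonged QTc is less likely to choose ondansetron.

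**The case against.** The strongest reply is that leaving a drug unbarred is not the same as directing its use. The paragraph steers clinicians towards another antiemetic and explains why it stops short of a ban: some infants are on placebo. Care rests with attending physicians under standard of care (section 6.2), who would know of the QTc reading. The study team visits daily and checks that the clinical team understands the protocol. Well Baby Nursery infants with a heart rate below 80 have a rhythm strip or ECG, and NICU infants are on continuous ECG. All of this stands, and it is why the point is minor. It does not remove the problem that the protocol's one statement about the harm of extra ondansetron is unqualified and sits badly with its own safety stop.

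Three stronger readings are tempting, and the documents do not support them.

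- A reader might infer that section 5.0 contradicts the reassurance, because it describes ondansetron as little studied in neonates. The same entry also says the drug is used in infants and young children and regards the risk as minimal. The mismatch is one of certainty, not a contradiction.
- A reader might infer that the protocol applies a stricter safety standard before birth, because of this rule: "Maternal ingestion or administration of ondansetron within 24 hours prior to delivery, for reasons other than study purposes, will exclude the mother and neonate". No safety reason is given, and the trial itself gives mothers ondansetron. Keeping the placebo arm uncontaminated would explain the rule equally well.
- A reader might conclude that ondansetron should be barred for every neonate while study drug is being given. That would take an option from infants with a normal QTc, and an unnamed substitute could itself prolong the QT interval: a study in the protocol's reference list names droperidol alongside ondansetron for that effect.

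**Conclusion.** The point holds in a limited form. The QTc stop applies to study drug, and the nausea paragraph leaves clinical ondansetron open, with a reassurance about harm that makes no exception for a stopped infant. The documents do not show that anyone is told to give ondansetron to an infant with a prolonged QTc, or that such an infant would go unmonitored.

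The practical size is small: fewer than one infant among 120 on the rates assumed above, which are not taken from the documents. The event could be serious and the remedy costs little, so the change is worth making as a minor safety improvement.

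Confidence is moderate. Part of the claim is that no prohibition exists, and two sources could not be checked: the protocol text between sections 2.1.2 and 4.0, and the site guidelines described as attached. The protocol notes that the DSMB review of the first 20 pairs took place in April to May 2016, but its findings are not given.

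**What to change.** In section 2.1.1 C, neonatal item 2, with cross-references in sections 2.1.2 and 6.2:

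1. State that an infant with QTcB of 480 ms or more, or stopped for ECG changes, is not to receive ondansetron from any source during the study unless the QTc has normalised and the treating physician or a cardiologist agrees.
2. State that any alternate antiemetic for such an infant should be chosen with its QT effect in mind.
3. Delete the sentence saying an additional dose is harmless, or limit it to infants with a normal QTc.
4. Leave the advisory wording on alternate antiemetics unchanged for all other neonates.

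The cost is a few sentences. Study dose, ECG schedule, sample size and analysis are unaffected. The downside is that a stopped infant, including one on placebo, loses one antiemetic option until the QTc recovers.

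The SAP is dated March 30, 2022 and written in the past tense, so enrolment may be complete. In that case new wording protects no one, and the report should instead say whether any infant received non-study ondansetron and whether any did so after QTcB of 480 ms or more. This may require a look at medical records, because the neonatal data list in section 4.3 covers medications for NAS and does not clearly capture an antiemetic given for nausea.
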